6.1 Overview

This section presents the analytical approach for the Cerridwen efficacy study.⁹

All analysis will be conducted once delivery comes to an end in April 2025. Analysis will be conducted on an intent-to-treat basis in line with YEF guidance. This means that all participants will be analysed according to their allocation, regardless of whether they received the Cerridwen intervention or not. This provides the most conservative estimate of impact, as this approach evaluates the impact of offering the intervention to those who do and do not comply and helps to fully capture the 'true' benefit (if any) of the intervention (Torgerson and Torgerson, 2008). This approach is particularly relevant for policymakers and commissioners, i.e. those who may roll out an intervention but do not have control over take-up of the intervention across the system.

The analytical approach has been developed a priori and will be conducted in SPSS 25.¹⁰

6.2 Primary outcome analysis

The primary outcome is the volume of offending at the individual level as measured by the self-reported delinquency scale (SRDS; Smith & McVie, 2003), completed before randomisation and at five-months post randomisation. Young people are asked to report behaviours they have been involved in over the previous five months.

There is considerable debate about best practice when it comes to the analysis of data from RCTs. For example, Twisk et al. (2018) advocate for utilising longitudinal analysis of covariance or a repeated measures analysis without the treatment variable, but with the interaction between treatment and time in the model controlled for. They argue that failure to control for baseline differences in outcomes between the groups can lead to biased treatment estimates. Alternatively, others have cautioned against this approach (Sen, 2013).

Based on our understanding of such literature, our analysis of the impact of the Cerridwen programme on the SRDS volume score will be conducted using a fixed effects analysis of covariance (ANCOVA) model, controlling for baseline SRDS score and site. The ANCOVA analysis will calculate the mean difference in SRDS scores between young people who received support from Cerridwen (the treatment group) and those who received 'light touch' wellbeing

⁹ In line with YEF requirements this plan has been written before all baseline data for the efficacy study has been collected.

¹⁰ IBM Corp. Released 2017. IBM SPSS Statistics for Windows, Version 25.0. Armonk, NY: IBM Corp.

support (the control group), whilst accounting for baseline SRDS score and site. The outputs from this analysis will be used to calculate the Hedges' G effect estimate (described in Section 6.11). We have adjusted for site because Cerridwen, although managed by one central team, is being delivered in three areas (Cardiff, Merthyr Tydfil, Swansea and Caerphilly) by areaspecific case managers who do not work across multiple sites. Adjusting for site will therefore help isolate and understand the influence of location-specific factors (such as geographic variation and staff influence) on the primary outcome.

We will use the following model:

$$Y_i = \beta_0 + \beta_1 Baseline_i + \beta_2 Group_i + \delta Area_k + \varepsilon_i \in N(0, \sigma^2)$$

For i = 1, ..., n young people per area, and k = 1, ..., K Area

Where:

- Y_i is the T2 (five months post-randomisation) volume score for self-reported delinquency as measured by the SRDS.
- Baseline_i is the baseline outcome measure of the SRDS volume score for young person
 i.
- $Group_i$ is a dummy variable for allocation group, i.e. 1 for the treatment group and 0 for the control group.
- β_2 is the average treatment effect, i.e. the primary parameter of interest for the trial.
- $Area_k$ is a vector of K-1 binary area dummy variables.
- ε_i is the error/residual.
- σ^2 is the variance.

Specifying this model upfront will help to ensure that the analyses avoid the "fishing problem" and the "curse of dimensionality" (Humphreys et al 2013; Hayes, 2011).

We will also run robustness checks to assess the underlying assumptions for ANCOVA (e.g., linearity, homogeneity of regression slopes, normality of residuals, homoscedasticity) before conducting this analysis to ensure the proposed approach is appropriate. This will include assessing normality of the data using histograms and K-S tests. If the data does not meet these assumptions, we will run a non-parametric ANCOVA analysis. This will be determined once all data has been collected.

It is possible that the baseline and outcome variables may be skewed. Skew will be assessed using the traditional criteria based on their distribution (i.e., skews of greater or equal to 1.0

or less than or equal to -1.0). We will make a final decision about the best approach to address skew once this has been identified in the final data set. However, research suggests that the Tobit or two-part approach might be most appropriate (Boulton & Williford, 2018).

6.3 Secondary outcomes analysis

Our approach to analysis of secondary outcomes will mirror the approach outlined above for primary outcome analysis.

The secondary outcomes are:

- Ability to understand and/or experience the emotions of others (empathy), as measured by the Basic Empathy Scale (BES) (Jolliffe and Farrington, 2006) at baseline and T2 (five months post-randomisation).
- Pro-social values and behaviours measured by the Strengths and Difficulties Questionnaire pro-social behaviour subscale (SDQ) (Goodman, 2005) at baseline and T2 (five months post-randomisation).
- Behavioural difficulties, measured by the Strength and Difficulties Questionnaire externalising behaviours scale (SDQ) (Goodman, 2005) at baseline and T2 (five months post-randomisation).

For each secondary outcome we will conduct analyses of impact on the measures outlined above. This will be conducted using the same ANCOVA model specified for the primary outcomes measure outlined in Section 6.2 Primary outcome analysis above, which will include the baseline measurement for the respective secondary outcome variable where relevant.

We will also run robustness checks to assess the underlying assumptions for ANCOVA for each secondary outcome measure. This will include assessing normality of the data using histograms and K-S tests. If the data does not meet these assumptions, we will run a non-parametric ANCOVA analysis. This will be determined once all data has been collected.

These analyses will be conducted in SPSS 25.¹¹

6.4 Subgroup analyses

The subgroup analyses we plan to undertake are likely to be exploratory in nature. Before undertaking any sub-group analyses, we would assess whether these would be sufficiently powered based on the data we have collected. If any subgroup analysis is not sufficiently powered, the analysis would be reported as exploratory, and any results caveated to be interpreted with caution.

We will assess the presence of heterogenous treatment effects in line with race equity, equality, diversity and inclusion considerations. There is limited evidence about the relative effectiveness of mentoring programmes for those from minority ethnic backgrounds. As such, we will explore whether it might be possible to evaluate whether the Cerridwen intervention was equally effective for those from racially minoritised backgrounds compared to those from White backgrounds. This would likely be an underpowered analysis so caution should be applied when interpreting the results.

We will conduct this ANCOVA analysis by exploring the presence of interaction effects between ethnicity and treatment allocation. We will report the estimated differences across subgroups with the respective confidence intervals. This would use the following model:

$$Y_i = \beta_0 + \beta_1 Baseline_i + \beta_2 Group_i + \gamma Area_k + \delta Ethnicity_{ij} + \theta Ethnicity_{ij} * Group_i + \varepsilon_i \in N(0, \sigma^2)$$

For $i=1,\ldots,n$ young people per area, with $j=1,\ldots,J$ ethnicities, in $k=1,\ldots,K$ areas

¹¹ IBM Corp. Released 2017. IBM SPSS Statistics for Windows, Version 25.0. Armonk, NY: IBM Corp.

This model uses the same variables as the model set out in Section 6.2 Primary outcome analysis. In addition:

- $Ethnicity_{ij}$ is a vector of binary dummy variables for J-1 ethnicities.
- θ is a vector of parameters indicating the existence of heterogenous treatment effects by ethnicity. The total treatment effect for young people in each ethnicity grouping will be $\beta_2 + \theta$.

We will report both the point estimates and confidence intervals for θ . If θ indicates that the Cerridwen intervention is differentially impactful for different ethnicities, we will also consider re-running the model in Section 6.2 Primary outcome analysis for each sub-group separately (i.e. for young people from White, Asian, Black, Mixed and Multiple ethnic backgrounds, and Other ethnic backgrounds). If the two treatment effects are similar, this will strengthen the findings from this exploratory analysis.

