6.8 Missing data

Throughout the trial, the evaluation team will work closely with the Cerridwen intervention team to support the collection of high quality and complete data for all young people. However, missing data may arise due to either item non-completion or sample attrition (i.e. young people who do not complete all items of the baseline or the T2 questionnaires). We will assess both the extent of missingness and patterns of missingness in the data. In line with YEF guidance (2021a) we will report on both: (1) the proportion of missing data in the trial, and (2) the extent and pattern of missingness in the data. This will involve analysis of whether data is missing completely at random (MCAR), missing at random (MAR), or missing not at random (MNAR). MCAR and MAR mean that complete cases are unlikely to be biased subsequent to adjustment but may be underpowered, while MNAR suggests that structural bias has been introduced to the sample.

We will attempt to establish the missing mechanism (i.e. which variables in the data are predictive of non-response) through logistic regression models. This will model the presence of missing outcomes data with additional information that may be predictive of missingness. We will conduct this analysis in line with the flow chart in Figure 1 in the YEF analysis guidance (2021a). This outlines the following approach:

- If the prevalence of missing data is less than 5%, no further action is required as complete case analysis is unlikely to be biased.
- If outcomes data is MAR conditional on co-variates, we will include these co-variates in our primary analysis model and discuss the implications in full.
- If a covariate is MAR conditional on other covariates, we will conduct multiple imputation (MI). Treatment effects from the MI analysis will be reported in addition to estimates from the model outlined in Section 6.2 Primary outcome analysis. Any differences between the two and their implications will be discussed in full.

• If missing data cannot be fully explained by the other variables in the dataset, data is likely to be MNAR. In this scenario we will conduct a sensitivity analysis alongside the primary impact analyses.

We will only conduct the above analyses for the primary outcome analysis, as all secondary outcomes analysis, subgroup analysis and further analysis is tentative and exploratory in nature.

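### Section 6.4 counts agreement with subgroup re-runs on the same participants as added support, and has no joint test for its several ethnicity interactions

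*SAP*

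**What the plan says.** Section 6.4 sets out to explore "whether the Cerridwen intervention was equally effective for those from racially minoritised backgrounds compared to those from White backgrounds". That is one contrast between two groups.

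The model that follows adds ethnicity and its product with allocation to the primary ANCOVA. The ethnicity term "is a vector of binary dummy variables for J-1 ethnicities", and theta is the matching vector of interaction terms. J is not given as a number. The only list of groups comes with the re-runs: "young people from White, Asian, Black, Mixed and Multiple ethnic backgrounds, and Other ethnic backgrounds". That makes five groups and so four interaction terms.

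Point estimates and confidence intervals for theta are to be reported. If theta "indicates that the Cerridwen intervention is differentially impactful for different ethnicities", the plan will consider fitting the section 6.2 model in each group separately, and concludes: "If the two treatment effects are similar, this will strengthen the findings from this exploratory analysis". There is no joint test of theta, no threshold for the trigger, and no definition of similar effects.

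On status, section 6.4 says of subgroup analyses that "we would assess whether these would be sufficiently powered based on the data we have collected", and ties the exploratory label to an analysis failing that check. It also warns that the ethnicity analysis is likely to be underpowered and should be read with caution. Section 6.8 says without condition that "all secondary outcomes analysis, subgroup analysis and further analysis is tentative and exploratory in nature".

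**The concern.** There are three linked weaknesses.

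- **Agreement is read as evidence.** The re-runs use the same young people, outcome, baseline score and area terms as the interaction model, and are considered only once that model has signalled a difference. A chance difference in the data will appear in both fits.
- **The model does not answer the stated question.** No single theta compares minoritised with White young people. With several thetas and no joint test, the opportunity for a chance signal grows with the number of groups.
- **The label is not settled.** Section 6.4 makes the exploratory label depend on a power check; section 6.8 does not.

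At stake is how the trial answers research question 2b in section 4.2, on whether outcomes differ between subgroups. A chance difference in a small ethnic group could be reported with more confidence than the data support.

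**Working it through.** **Inputs from the SAP.** Analysed sample 592, or 367 as the updated realistic figure (section 5.1); baseline/follow-up correlation 0.5 (section 5.1); two-sided alpha 0.05 (sections 5.1 and 6.11); 1:1 allocation (section 4.1); four areas; five listed ethnic groups (section 6.4).

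**Assumed.** The ethnic mix, for which the SAP has no figure: 80%, 70% or 50% White, the rest spread over four groups. Also a normal outcome, and that a 95% interval excluding zero counts as a signal from theta.

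**Step 1: the plan's own figure.** Participants per arm = 2 × (1.960 + 0.842)² × (1 − 0.5²) / 0.20² = 2 × 7.85 × 0.75 / 0.04 ≈ 294.3, so 295 per arm and 590 in all. The t-based formula with one covariate gives 591, with a minimum detectable effect of 0.1998 at 592 and 0.254 at 367. The SAP's 592 and its 0.25 at 367 are reproduced. It gives no figure for the ethnicity interaction.

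**Step 2: false signals from reading the thetas singly.** For four independent terms, 1 − 0.95⁴ = 0.185. The terms share the White reference group, so the section 6.4 model was also simulated with no effect in any group (4,000 trials per scenario; both sample sizes and all three mixes).

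| Rule | Chance of a false signal |
|---|---|
| Any of four 95% intervals excludes zero | 18.2 to 18.5% |
| One joint test of theta (4 df) | 4.4 to 5.6% |
| One White-versus-minoritised interaction | 4.6 to 5.2% |

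A further mix of 75/7/6/8/4% at 367 stays within about 18 to 20% for the first rule.

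**Step 3: what the re-run adds.** In the same null trials, whenever a theta was falsely flagged, the group's effect from the interaction model was compared with its effect from the separate model.

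| Quantity | Sample 592 | Sample 367 |
|---|---|---|
| Correlation of the two estimates | 0.985 to 0.994 | 0.964 to 0.990 |
| Contrast with White keeps its direction | 100% | 99.4 to 100% |
| Estimates within 0.2 SD | 88 to 100% | 66 to 98% |

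Every signal here was chance, yet the re-run almost always pointed the same way and was usually close in size.

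**Step 4: the other reading of the sentence.** If the two effects meant those in two ethnic groups, similarity would contradict the heterogeneity that prompted the re-run. The sentence fails on that reading too.

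**Step 5: power of a single contrast.** With minoritised share p, SE = √[0.75 × (4/N) × (1/p + 1/(1 − p))]. For N = 592 and p = 0.2 this is √(0.005068 × 6.25) = 0.178. Power for a 0.20 SD difference is Φ(0.20/0.178 − 1.96) plus a negligible lower tail, about 20%. For p of 10%, 20%, 30% and 50%, power is 13%, 20%, 25% and 29% at 592, and 10%, 14%, 17% and 20% at 367. Even the simplest contrast must stay exploratory.

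**The case against.** The strongest reply has five parts.

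- **The re-run is not empty.** The interaction model imposes one baseline slope, one set of area effects and one residual variance on all groups; separate models relax all three. This stands: agreement is a fair model-sensitivity check. It is not further evidence that the difference is real.
- **Agreement is not certain.** A reader might infer that every chance finding would be confirmed. That is too strong. With the 75/7/6/8/4% mix at 367, a falsely flagged group's two estimates were within 0.2 SD in 77% of cases, and the re-run itself reached p < 0.05 in 45%. With a log-normal outcome these fall to 51% and 23%. The re-run is also only to be considered.
- **The label is unlikely to be lost.** A reader might infer that a chance result could be promoted out of exploratory status. The SAP's own text and figures do not support this: the criticised sentence itself calls the analysis exploratory, section 6.4 expects low power, and step 5 agrees. What remains is a wording mismatch between sections 6.4 and 6.8.
- **Four tests are not stated.** Section 6.4 promises estimates and intervals and names no p-value rule. Four terms and the trigger are inferred, so the 18 to 20% is conditional on both.
- **One contrast should not replace the five-group model.** At 367, a 0.5 SD difference in every minoritised group gives 66% power for the single contrast and 42% for the joint test. If only one group of 7% differs, by 1.0 SD, it is 25% against 56%. Research question 2b concerns subgroups in the plural, so both are needed.

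**Conclusion.** The point holds in limited form. The closing sentence of this analysis in section 6.4 states a rule that misleads if followed, because similarity between the two fits barely separates a real difference from a chance one. The direction result is firm under every mix tried; closeness in size is weaker in small groups and with skewed data.

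The lack of a joint test is a real gap. Its size, about 18 to 20% instead of 5%, rests on five ethnic groups, on any interval excluding zero counting as a signal, and on assumed ethnic shares, to which the rate is insensitive.

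The consequence is confined to how an exploratory equity result is interpreted. The primary analysis and the sample size are unaffected. The change is worth making because the existing caution about power does not cure a sentence that says when findings gain strength.

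**What to change.** 1. Delete the sentence on strengthened findings, or reword it to say that the separate-group models are a descriptive model-sensitivity check that adds no independent evidence.
2. Keep the five-group interaction model, state J, and make one joint test of theta the trigger for any statement that effects differ by ethnicity.
3. Add one pre-specified White-versus-minoritised interaction contrast with its 95% confidence interval, to answer the question that section 6.4 poses.
4. Report group-specific estimates and intervals descriptively.
5. Align section 6.4 with section 6.8, so that every subgroup result is labelled exploratory whatever the power check shows.

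The cost is a few lines of SAP text, one contrast and one joint test. No extra data are needed. The contrast alone could hide differences between minoritised groups; keeping the five-group model and its joint test guards against that.

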6.5 Further analyses

We will conduct the following exploratory subgroup analyses:

• The impact of positive relationships. We will evaluate the extent to which positive relationships between the young person and case manager (treatment group), or significant adult (control group) influenced the primary outcome over and above the impact of the Cerridwen Intervention (as measured by the SSRS — see call-out box below). This analysis is proposed because the Cerridwen theory of change suggests that a key mechanism of change for the intervention is that it has its effect through an increase in positive relationships with a trusted adult. This will take a mediation analysis approach, i.e. we will estimate the direct and indirect effects, following the approach outlined in Gunzler et al. (2013).

About the Social Support and Rejection Scale (SSRS)

The **SSRS** has four dimensions: Feels valued, trust, mentoring, and negativity. Each item is scored from 1 (never) to 5 (always). Each subscale score is the average of items that make up the subscale. Higher scores on the negativity scale reflect higher levels of stress and negativity within the relationship. For the overall scoring of the scale a high score represents a positive relationship.

Dosage and fidelity. Fidelity to the model will be measured by the number and type of
sessions participants receive, as well as how much time they are involved in Cerridwen.
This will be compared to Cerridwen's theory of change and its intended delivery model.
Any analysis relating to dosage and fidelity will be exploratory in nature. If power
calculations suggest that this analysis would be sufficiently powered, we will explore

the associations between activities received as part of Cerridwen the level of dosage and the impact on the SRDS Volume score. This data will be captured by monitoring data on the number of sessions, and time received by Cerridwen participants collected by the Cerridwen delivery team. This analysis will be conducted using a general linear model assuming normality, or a generalized linear model. Possible variables will include the number of sessions received and the time period over which they were received. This approach would address questions such as: does attending eight or more Cerridwen sessions result in a similar impact as attending all sessions?

- The impact on police contacts. We will also explore the possibility of analysing reduced offending as measured by police data. We anticipate requesting data on police contacts, including type and timing of events (e.g., police contact, arrest, recorded offences, and convictions, all with associated dates). However, final data availability will be determined based on discussions with data providers. If we are able to access robust and reliable police data, we will explore whether Cerridwen had an impact on reducing contacts with police over and above that reported in the control group. This analysis would be conducted using a general linear model, repeated measures design (assuming normality) or a generalized linear model. We will include a treatment by outcome interaction term in the analysis. We will only proceed with this analysis if power calculations suggest these analyses would be sufficiently powered.
- **Exploration of unintended negative effects.** Through the analysis outlined in this SAP we will also explore whether the programme has any negative impacts on young people. We will triangulate this with data collected through the IPE.

6.6 Interim analyses and stopping rules

After the first cohort of baseline data collection we will analyse the completeness, reliability and validity of outcomes questionnaires (including the outcomes measures described above). We will do this by exploring:

- Percentages of scale item completeness.
- Outcome measure means, standard deviations and skew.
- Cronbach Alpha testing for scale reliability.

This analysis will not include a comparison between control group and treatment group data nor analysis of impact. We will review and discuss these findings with MAC and YEF to provide reassurance that data collection is proceeding well. If there are concerns, we will suggest and discuss solutions with YEF and MAC.

We will continue to monitor data quality looking at scale completeness, means, standard deviations and skew throughout the trial for internal purposes to ensure that data collection proceeds smoothly. If, on review, we have concerns, we will raise this with YEF and MAC as appropriate.

The trial will stop if the Cerridwen is unable to recruit a sufficient number of participants. Recruitment rates will be regularly monitored against modelled target rates and reviewed as part of project group meetings. In addition to recruitment concerns, attrition rates will also be monitored throughout the trial. Given the importance of minimising bias due to participant dropout, we will track:

- Overall attrition the percentage of participants lost between baseline and endline.
- Differential attrition differences in attrition rates between treatment and control groups.

Stopping decisions will be guided by YEF's evidence quality framework. If attrition exceeds 31%, we will assess the implications for statistical power and risk of bias with YEF and MAC colleagues. If attrition is high but manageable, we will consider mitigation strategies such as sensitivity analysis or imputation. However, if attrition reaches a level where the study can no longer produce meaningful findings, we will discuss stopping the trial with YEF and MAC colleagues. Any decisions about stopping will be made in discussion with YEF and MAC colleagues.

The Cerridwen project team will also be responsible for safeguarding of participants. They will report any serious adverse events overall and by trial arm. The trial will stop if MAC, YEF and Cordis Bright decide that the Cerridwen intervention is unsafe for participants.

